## 2 SYNOPSIS

Protocol Title:	A Phase 2b Open-Label Study to Evaluate the Safety, Tolerability, Pharmacokinetics, and Pharmacodynamics of FAST PV and mGFR Technology™ in Healthy Subjects and Patients with Varying Degrees of Renal Impairment
Study Phase:	2b
Indication:	Quantitative determination of plasma volume (PV) and measured glomerular filtration rate (mGFR)
Investigators and Clinical Research Units:	
Cohorts 1 and 2: [name] ICON Early Phase Services, LLC
 
Cohort 3: [name] University of Alabama Birmingham [name] ICON Early Phase Services, LLC
 
Cohort 4: [name] University of Alabama Birmingham

Objectives:	
Primary:
 

• To assess the safety and tolerability of visible fluorescent injectate (VFI)™ (employing the FAST PV and mGFR Technology™) compared to Iohexol (employing Iohexol clearance methods) in healthy subjects and patients with impaired renal function

• To evaluate the pharmacokinetics (PK) of FD001 and FD003 in healthy subjects and patients with impaired renal function

• To evaluate the PK of FD001 and FD003 in healthy subjects receiving 2 doses of VFI separated by 24 hours to evaluate the reproducibility of the FAST mGFR Technology.

 
Secondary:
 

• To evaluate the relationship between FAST PV and mGFR Technology and standard clinical formulaic estimates of PV in healthy subjects

• To evaluate and compare glomerular filtration rates (GFRs) determined from FAST PV and mGFR Technology and Iohexol clearance in healthy subjects and patients with impaired renal function

• To evaluate the GFR measurements in relation to current clinical standards in healthy subjects and patients with impaired renal function

• To evaluate the FAST PV Technology's ability to measure changes in vascular plasma volume resulting from a fluid challenge after the baseline PV measurement

Hypotheses:	This is an exploratory pilot investigation without any formal statistical hypotheses. All results will only be interpreted descriptively. Correlation analysis and Bland-Altman plots will be used to compare the FAST mGFR with Iohexol clearance.

CONFIDENTIAL

**Endpoints:**

Primary:

Safety:

- Adverse events (AEs) and serious AEs (SAEs)
- Clinical laboratory tests, physical examination findings, 12-lead electrocardiograms (ECGs), and vital signs including pulse oximetry

Pharmacokinetics:

- Maximum observed plasma concentration ( $C_{max}$ )
- Time that  $C_{max}$  was observed ( $t_{max}$ )
- Area under the plasma concentration-time curve (AUC) from time 0 to 12 hours ( $AUC_{0-12}$ ; FD001 only)
- AUC from time 0 to the time of the last quantifiable concentration ( $AUC_{last}$ )
- AUC from time 0 extrapolated to infinity ( $AUC_{inf}$ )
- Terminal elimination half-life ( $t_{1/2}$ )
- Terminal elimination rate constant ( $\lambda_z$ )
- Total body clearance (CL)
- Renal clearance from time 0 to 2 hours ( $CL_{r0-2}$ ; FD001 only)
- Renal clearance from time 2 to 12 hours ( $CL_{r2-12}$ ; FD001 only)
- Renal clearance from time 0 to 12 hours ( $CL_{r0-12}$ ; FD001 only)
- Volume of distribution during the terminal phase ( $V_z$ )
- Volume of distribution at steady state ( $V_{ss}$ )
- Amount of FD001 excreted unchanged in the urine from time 0 to 2 hour ( $Ae_{0-2}$ )
- Amount of FD001 excreted unchanged in the urine from time 2 to 12 hour ( $Ae_{2-12}$ )
- Amount of FD001 excreted unchanged in the urine from time 0 to 12 hour ( $Ae_{0-12}$ )

Secondary:

Pharmacodynamic:

- PV as assessed by FAST PV and mGFR Technology
- PV as assessed by Nadler's formula
- Assess changes in PV after fluid challenge
- Assess repeatability of GFR measurements over 24 hours
- mGFR as assessed by FAST VFI and Iohexol clearance methods
- Estimated GFR (eGFR) (calculated by the Modification of Diet in Renal Disease [MDRD], Chronic Kidney Disease Epidemiology Collaboration [CKD-EPI] Creatinine, and Cockcroft-Gault equations)

**Study Design:**

This is a Phase 2b, prospective, open-label study designed to evaluate the safety, tolerability, PK, and pharmacodynamics (PD) of FAST PV and mGFR Technology in healthy subjects and patients with varying degrees of renal impairment.

For Cohorts 1 and 2, administration of the study drug will occur within 21 days of screening. Eligible subjects will be admitted to the clinical research unit (CRU) on Day -1, at which time assessments will be performed, and results from both screening and Day -1 (inclusion/exclusion criteria, body weight, height [screening only], body mass index [BMI], medical and surgical history, physical examination, vital signs and pulse oximetry, 12-lead ECG, clinical laboratory tests, renal function assessment, follicle-stimulating hormone [FSH; screening only] and pregnancy test [females only], urine drugs of abuse, and serum alcohol screen) will be reviewed to confirm eligibility.

CONFIDENTIAL

**Study Design:  
continued**

For Cohorts 3 and 4, administration of the study drug will occur within 21 days of screening.

Eligible patients enrolled at UAB will be admitted to the CRU on Day 1, at which time assessments will be performed and results from both screening and predose administration testing (inclusion/exclusion criteria, body weight, height [screening only], BMI, medical and surgical history, physical examination, vital signs and pulse oximetry, 12-lead ECG, clinical laboratory tests, renal function assessment, FSH [screening only] and pregnancy test [females only], urine drugs of abuse, and serum alcohol screen) will be reviewed to confirm eligibility.

Eligible patients enrolled into Cohort 3 at ICON Early Phase Services, LLC will be admitted to the CRU on Day -1 and will remain resident in the CRU through discharge on Day 2. Eligible subjects will be admitted to the clinical research unit (CRU) on Day -1, at which time assessments will be performed, and results from both screening and Day -1 (inclusion/exclusion criteria, body weight, height [screening only], body mass index [BMI], medical and surgical history, physical examination, vital signs and pulse oximetry, 12-lead ECG, clinical laboratory tests, renal function assessment, follicle-stimulating hormone [FSH; screening only] and pregnancy test [females only], urine drugs of abuse, and serum alcohol screen) will be reviewed to confirm eligibility.

The planned dose cohorts are presented in the table below:

Cohort	eGFR	VFI Dose	Number of Doses	Comparator Dose	Number of Doses	Number of Subjects
1*	$\geq 60$ mL/min/1.73 m 	47 mg/3 mL	1	---	---	Up to 8
2	$\geq 60$ mL/min/1.73 m 	47 mg/3 mL	2	Iohexol 5 mL	1	Up to 8
3	$\geq 30$ and $< 60$ mL/min/1.73 m 	47 mg/3 mL	1	Iohexol 5 mL	1	Up to 8
4	$\geq 15$ and $< 30$ mL/min/1.73 m 	47 mg/3 mL	1	Iohexol 5 mL	1	Up to 8

\*Subjects in Cohort 1 will receive a volume challenge

Cohort 1:

Eligible subjects  $\geq 50$  kg in weight will receive a single dose of VFI followed 130 minutes later by a 350 mL infusion of 5% albumin over 30 minutes on Day 1. Eligible subjects  $< 50$  kg in weight will receive a single dose of VFI followed 130 minutes later by a maximum infusion of 5% albumin of 7 mL/kg over 30 minutes on Day 1. Subjects will remain resident in the CRU for at least 24 hours after VFI administration for safety assessment. Subjects will return to the CRU for an end-of-study (EOS) visit on Day 21 ( $\pm 1$  day).

Cohort 2:

Eligible subjects will receive a dose of VFI followed 160 minutes later by a single dose of Iohexol on Day 1 and a second dose of VFI 24 hours (on Day 2) after the initial dose of VFI. Subjects will remain resident in the CRU for at least 24 hours after the second VFI administration for safety, PK, and PD assessments. Subjects will return to the CRU for follow-up visits on Days 5 ( $\pm 1$  day), 9 ( $\pm 1$  day), and 16 ( $\pm 1$  day), and an EOS visit on Day 22 ( $\pm 1$  day).

Cohorts 3 and 4:

Eligible patients will receive a single dose of VFI followed 160 minutes later by a single dose of Iohexol on Day 1.

CONFIDENTIAL

**Study Design:  
continued**

Patients enrolled into Cohort 3 at ICON Early Phase Services will remain resident in the CRU for at least 24 hours after VFI administration for safety, PK, and PD assessments. Patients will return to the CRU for follow-up visits on Days 4 ( $\pm$  1 day), 8 ( $\pm$  1 day), and 15 ( $\pm$  1 day), and an EOS visit on Day 21 ( $\pm$  1 day).

Patients enrolled into Cohorts 3 or 4 at UAB will remain in the CRU through the 12-hour sample collection after VFI administration for safety, PK, and PD assessments. Patients will stay at a local hotel near the CRU and will return to the CRU on Day 2 for 24-hour sample collection. Patients will return to the CRU for follow-up visits on Days 4 ( $\pm$  1 day), 8 ( $\pm$  1 day), and 15 ( $\pm$  1 day), and an EOS visit on Day 21 ( $\pm$  1 day).

**Subject Selection  
Criteria:**

Males and females (women must be post-menopausal or be using a medically acceptable form of birth control) 18 to 75 years of age, inclusive, with a body weight of at least 40 kg will be enrolled in the study. Reproductively active men must agree to either practice abstinence or utilize adequate contraception. Healthy subjects in Cohorts 1 and 2 must have an eGFR calculated using the CKD-EPI Creatinine Equation (2009)  $\geq$  60 mL/min/1.73 m^2 and a BMI of 18.0 to 40.0 kg/m^2, inclusive. Patients with impaired renal function in Cohort 3 must have an eGFR  $\geq$  30 and  $<$  60 mL/min/1.73 m^2 and patients with impaired renal function in Cohort 4 must have an eGFR  $\geq$  15 and  $<$  30 mL/min/1.73 m^2. Patients in Cohorts 3 and 4 must have a BMI of 18.0 to 40.0 kg/m^2, inclusive.

**Investigational  
Product, Dose, and  
Route of  
Administration:**

VFI, 47 mg/3 mL, bolus injection (35mg of FD001 and 12mg of FD003)

**Comparator Products,  
Dose, and Route of  
Administration:**

Omnipaque™ 300 (Iohexol), 5 mL, bolus injection (Cohorts 2 through 4)

**Criteria for Evaluation:****Safety:**

Adverse events (AEs) will be collected and evaluated as they occur throughout the study. Safety assessments, including physical examinations, vital signs including pulse oximetry assessments, 12-lead ECGs, and clinical laboratory tests, will be performed at specified time points.

**Pharmacokinetics:** Pharmacokinetic samples for plasma FD001 and FD003 concentration determination in Cohort 1 will be collected predose and 15, 30, 60, 120, 165, 195, 205, 310, 370, and 480 minutes and 12 and 24 hours post VFI dose. Pharmacokinetic samples for plasma FD001 and FD003 concentration determination in Cohort 2 will be collected predose and 15, 30, 60, 120, 170, 310, 370, and 480 minutes, 12 and 24 hours post VFI dose on Days 1 and 2, and on Days 5 ( $\pm$  1 day), 9 ( $\pm$  1 day), 16 ( $\pm$  1 day), and 22 ( $\pm$  1 day). Pharmacokinetic samples for plasma FD001 and FD003 concentration determination in Cohorts 3 and 4 will be collected predose and 15, 30, 60, 120, 170, 310, 370, and 480 minutes, 12, 24, and 32 hours post VFI dose, and on Days 4 ( $\pm$  1 day), 8 ( $\pm$  1 day), 15 ( $\pm$  1 day), and 21 ( $\pm$  1 day). Pharmacokinetic samples for urine FD001 concentration determination in Cohorts 2 through 4 will be collected predose, from dosing (0 hour) to 2 hours postdose, and from 2 to 12 hours postdose. Subjects in Cohort 2 receiving a second VFI dose on Day 2 will follow the same urine collection schedule as Day 1.

Plasma concentrations of FD001 and FD003 will be determined using a validated fluorometric assay.

CONFIDENTIAL

**Criteria for Evaluation:** Urine concentrations of FD001 will be determined using a validated method and concentration of FD001 will be multiplied by urine volume to determine the amount of excreted FD001.

The following PK parameters will be calculated from the plasma and urine concentration/volume data using noncompartmental methods and actual sampling times:  $C_{max}$ ,  $t_{max}$ ,  $AUC_{0-12}$  (FD001 only),  $AUC_{last}$ ,  $AUC_{inf}$ ,  $t_{1/2}$ ,  $\lambda_z$ ,  $CL$ ,  $CL_{r0-2}$  (FD001 only),  $CL_{r2-12}$  (FD001 only),  $CL_{r0-12}$  (FD001 only),  $V_z$ ,  $V_{ss}$ ,  $Ae_{0-2}$ ,  $Ae_{0-12}$ .

**Pharmacodynamics:**

Plasma Volume (Cohorts 1 through 4): Plasma volume will be determined using FAST PV Technology.

Additionally, PV will be estimated using Nadler's formula.

Glomerular Filtration Rate (Cohort 1): Measured GFR will be determined using FAST mGFR Technology.

Glomerular Filtration Rate (Cohorts 2 through 4): Measured GFR will be determined using FAST mGFR Technology and Iohexol clearance methods. Correlation analysis and Bland-Altman plots will be used to compare the FAST mGFR with Iohexol clearance.

Additionally, eGFR will be calculated primarily using the CKD-EPI equations, with additional calculations being performed using the MDRD and Cockcroft-Gault equations (Cohorts 1 through 4).

**Planned Sample Size:** Approximately 32 subjects/patients will be enrolled in 4 cohorts consisting of up to 8 subjects/patients each. Only subjects in Cohorts 2 through 4 will contribute to the plasma concentration PK statistical analysis; plasma concentrations for subjects in Cohort 1 will be analyzed for  $CL_r$ ,  $C_{max}$ , and using the FAST mGFR and PV measurement calculations only.

The sample size in this study is representative of Phase 2b studies of this type. Power calculations were not used to derive the sample size.

**Statistical Analysis:**

**Analysis Populations:**

Pharmacokinetic Full Population: All subjects in Cohorts 2 through 4 who receive a known amount of study drug and have at least one quantifiable concentration of FD001 or FD003 in plasma or FD001 in urine and all subjects in Cohort 1 who receive a known amount of study drug. Plasma concentrations for subjects in Cohort 1 will not contribute to the overall PK statistical analysis and will be analyzed for  $CL_r$ ,  $C_{max}$ , and using the FAST mGFR and PV measurement calculations only.

Pharmacokinetic Evaluable Population: All subjects in Cohorts 1 through 4 who receive a known amount of study drug and have at least 1 estimable PK parameter.

Safety Population: All subjects who received any amount of study drug.

Pharmacodynamic Evaluable Population: All subjects in Cohorts 1 through 4 who have either a PV or GFR estimate using any of the techniques under study. Subjects in Cohort 1 will not contribute to the overall PD statistical analysis.

CONFIDENTIAL

**Statistical Analysis:  
continued**

**Pharmacokinetic Analysis:** For Cohorts 2 through 4, subject plasma concentration-time profiles will be listed and summarized for each analyte by nominal sampling time.

Summary statistics will be listed and summarized for each PK parameter by cohort and analyte. Plasma concentrations for subjects in Cohort 1 will not contribute to the overall PK statistical analysis and will be analyzed for  $CL_r$ ,  $C_{max}$ , and using the FAST mGFR and PV measurement calculations only.

**Pharmacodynamic Analysis:**

**Plasma Volume (Cohorts 2 through 4):**

The FAST Technology for determining PV will be compared to PV estimated using Nadler's formula. Plasma volume data will be listed and summarized by presenting descriptive statistics of raw data. The correlation as well as the associated plot will be presented for comparing PV between methods. [Cosgriff et al. 1999](#) shows that a combination of the correlation and a histogram of the magnitude of difference is needed when no measured comparator is available. Subjects in Cohort 1 will not contribute to the overall PD statistical analysis.

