### **3.7       Hypotheses**

This is an exploratory pilot investigation without any formal statistical hypotheses. All results will only be interpreted descriptively. Correlation, analysis and Bland-Altman plots will be used to compare the FAST mGFR with Iohexol clearance.

CONFIDENTIAL

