### **10.1 Sample Size Calculation**

Approximately 32 subjects/patients will be enrolled in 4 cohorts consisting of up to 8 subjects/patients each.

The sample size in this study is representative of Phase 2b studies of this type. Power calculations were not used to derive the sample size.

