5.2 Secondary Objective(s)

- To evaluate the relationship between FAST PV and mGFR Technology and standard clinical formulaic estimates of PV in healthy subjects
- To evaluate and compare glomerular filtration rates (GFRs) determined from FAST PV and mGFR Technology and Iohexol clearance methods in healthy subjects and patients with impaired renal function
- To evaluate the GFR measurements in relation to current clinical estimated glomerular filtration rate (eGFR) equations in healthy subjects and patients with impaired renal function
- To evaluate the FAST PV Technology's ability to measure changes in vascular plasma volume resulting from a fluid challenge after the baseline PV measurement

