10.1.10 Analysis of Pharmacodynamic Data

10.1.10.1 Plasma Volume (PV)

The FAST PV Technology plasma volume (PV) will be compared to PV estimated using Nadler's formula. Plasma volume data will be listed and summarized by presenting descriptive statistics of raw data and for change in plasma volume.

Correlation analysis will be done for comparing the PV measured using FAST PV method and PV estimated using Nadler's Formula for each cohorts. Pearson product-moment correlation coefficient, standard error with 95% confidence interval of the coefficient will be provided.

In addition scatter plot will also be provided to support the correlation analysis. Also, histogram will be provided for the magnitude of difference (PV using FAST PV - PV estimated using Nadler's formula).

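### The documents conflict on whether Cohort 1 enters the FAST-versus-Nadler comparison, and on either reading no healthy-subject estimate uses more than 8 of the up to 16 healthy subjects

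*Protocol*

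**What the plan says.** **Objective.** SAP 5.2, like protocol 4.2, sets this aim: "To evaluate the relationship between FAST PV and mGFR Technology and standard clinical formulaic estimates of PV in healthy subjects".

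**Who is healthy.** The protocol synopsis identifies them in its selection criteria: "Healthy subjects in Cohorts 1 and 2 must have an eGFR calculated using the CKD-EPI Creatinine Equation (2009"), with a threshold of at least 60 mL/min/1.73 m². Cohorts 3 and 4 are renal patients.

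**Size.** Protocol 10.1: "Approximately 32 subjects/patients will be enrolled in 4 cohorts consisting of up to 8 subjects/patients each".

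**Analysis, protocol.** The synopsis paragraph on this comparison is headed "Plasma Volume (Cohorts 2 through 4") and closes with "Subjects in Cohort 1 will not contribute to the overall PD statistical analysis". The same exclusion stands in the population definitions of the synopsis, protocol 10.2 and SAP 10.1.4. Protocol 10.5.1, the body text on the same analysis, names no cohorts and has no exclusion.

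**Analysis, SAP.** SAP 10.1.10.1 states: "Correlation analysis will be done for comparing the PV measured using FAST PV method and PV estimated using" Nadler's formula, done cohort by cohort, with a 95% interval for Pearson's coefficient. It leaves no cohort out and also asks for summaries of change in PV.

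**Status of the study.** Protocol 3.7: "This is an exploratory pilot investigation without any formal statistical hypotheses". Protocol 10.1: "Power calculations were not used to derive the sample size".

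**The concern.** The objective names a population, and the analysis text does not deliver an estimate for it. The synopsis comparison covers up to 8 healthy subjects and up to 16 renal patients. The SAP comparison covers each cohort separately. Neither document plans one analysis of all healthy subjects.

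No stated reason for leaving Cohort 1 out applies to PV. The synopsis explains the exclusion from the GFR comparison by the absence of Iohexol in Cohort 1, but the Nadler comparison does not use Iohexol.

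At stake are two things. A programmer could include or omit Cohort 1 and cite the SAP either way. And the interval that the SAP commits to reporting will be wider than the collected data require.

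**Working it through.** **Step 1. The plan's own figure.** 4 cohorts × 8 = 32, which matches the stated total. Healthy subjects: 2 × 8 = 16 at most. Cohort 1 share: 8/16 = 50%. There is no power-based figure to reproduce.

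**Step 2. The passages side by side.**

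| Place | Cohort 1 in the PV comparison? |
|---|---|
| Protocol synopsis, PV analysis | No; limited to Cohorts 2 to 4 |
| Synopsis populations, protocol 10.2, SAP 10.1.4 | In the PD Evaluable Population, but outside the *overall* PD analysis |
| Protocol 10.5.1 | No restriction stated |
| Protocol 8.5.1.1, SAP 9.2.1.1 | FAST PV and Nadler PV both obtained in Cohorts 1 to 4 |
| SAP 10.1.10.1 | Yes, as its own cohort |
| SAP 10.1.10.2 (GFR) | Explicitly limited to Cohorts 2 to 4, because the comparator is Iohexol |

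Synopsis reading: the only healthy cohort is Cohort 2, so n is at most 8. SAP 10.1.10.1 reading: two separate healthy analyses, each with n at most 8. Neither gives n = 16.

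**Step 3. Is the Cohort 1 value usable?** Cohorts 1 and 2 get the same VFI dose (47 mg/3 mL) and have samples at 15, 30, 60 and 120 minutes with the same ±1 minute window (protocol Tables 2.4 and 2.5). Albumin starts at 130 minutes. The fluid-challenge objective itself relies on a baseline PV in Cohort 1. The documents do not list which samples feed the FAST PV calculation, so it is an assumption that samples up to 120 minutes suffice.

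**Step 4. Precision of the planned correlation.** Fisher's z interval: tanh(atanh(r) ± 1.96/√(n − 3)). The standard error on the z scale is 1/√5 = 0.447 for n = 8 and 1/√13 = 0.277 for n = 16. The documents give no expected r, so a range is assumed.

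| Assumed r | 95% CI, n = 8 | 95% CI, n = 16 |
|---|---|---|
| 0.5 | −0.32 to 0.89 | 0.01 to 0.80 |
| 0.7 | −0.01 to 0.94 | 0.31 to 0.89 |
| 0.8 | 0.22 to 0.96 | 0.50 to 0.93 |
| 0.9 | 0.53 to 0.98 | 0.73 to 0.97 |

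For r = 0.8 the width falls from 0.74 to 0.42.

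**Step 5. Precision of the mean difference.** The SAP plans a histogram of FAST minus Nadler, not an interval. If one were added, its half-width in SD units would be t(0.975, n − 1)/√n: 0.84 for n = 8 and 0.53 for n = 16, a reduction of 1 − 0.533/0.836 = 36%.

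**The case against.** A reader might infer that the plan drops Cohort 1, discards half of the healthy data, and lets the objective rest on 8 subjects. The documents do not support that. SAP 10.1.10.1 sets no cohort limit, whereas the next section does so explicitly for GFR. The PD Evaluable Population, which the PV table, scatter plot and histogram cite, includes Cohort 1 by definition. The change-in-PV summaries in SAP 10.1.10.1 most naturally concern the fluid challenge, which only Cohort 1 receives. The word *overall* in the exclusion sentence can be read as keeping Cohort 1 out of cross-cohort pooling only. On that reading Cohort 1 gets its own correlation and interval, and all healthy subjects are analysed. This part of the objection stands.

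It does not settle the matter. SAP 10.1.4 carries the exclusion sentence into the population that those outputs cite, and SAP Section 7 declares Nadler's formula to be the only change from the protocol. Nothing announces a departure from the synopsis. Even the favourable reading leaves two unpooled healthy groups.

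It is also fair to say that the study is exploratory and interpreted descriptively. That an interval with 8 subjects includes zero at r = 0.7 is therefore no failed test, since the plan applies no significance criterion. The width of an interval that the SAP promises to report remains relevant.

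**Conclusion.** The point holds as an inconsistency plus a gap. The inconsistency is between the exclusion of Cohort 1 (synopsis, protocol 10.2, SAP 10.1.4) and the healthy-subject objective together with the by-cohort analysis in SAP 10.1.10.1. The gap is that no pooled analysis of the healthy subjects is specified. It should not be put as discarded data.

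The consequence is lost precision and a poor fit to a secondary objective, with no bearing on power or type I error. Over the assumed correlations of 0.5 to 0.9, pooling shortens the interval by roughly 34% (1.207 to 0.792 at r = 0.5) to 48% (0.448 to 0.235 at r = 0.9). This rests on both cohorts filling to 8, on a FAST PV being obtainable from the samples up to 120 minutes, and on Cohorts 1 and 2 forming one healthy population, as the shared eligibility criteria imply.

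**What to change.** 1. Reconcile the exclusion sentences in the synopsis (populations and PV analysis), protocol 10.2 and SAP 10.1.4 with protocol 4.2 and SAP 10.1.10.1. Either clarify the protocol or record the departure in SAP Section 7.
2. For PV, limit the exclusion of Cohort 1 to data collected after albumin starts.
3. In SAP 10.1.10.1, specify the analysis for this objective as FAST versus Nadler in Cohorts 1 and 2 pooled, with one value per subject: Cohort 1 from samples up to 120 minutes, Cohort 2 from Day 1. The SAP does not now say which FAST PV value enters, so a post-albumin or Day 2 value could be used.
4. Show Cohorts 3 and 4 separately as supportive. Optionally add the mean difference with its 95% interval.

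Cost: SAP wording, a protocol clarification or a Section 7 note, and one extra column or panel in Table 14.2.3.1 and Figures 14.2.3.1 and 14.2.3.3. No new samples, visits or subjects are needed.
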